1. Inclusion Criteria: Patients with ocular hypertension or open angle glaucoma undergoing combined cataract surgery with trabectome in a single surgical center at Montefiore Medical Center with a single provider between March 1st 2018 and July 1st 2020
2. Exclusion Criteria: Patients with previous history of eye surgeries (including laser procedures).
3. Age Range: 30 to 100 years old

Study Design

Prospective randomized controlled trial

Study Methods

140 consecutive patients with POAG who are planned for combined cataract/trabectome surgeries will be consented for inclusion in this study. Patients will be randomized to one of two study arms, using an online computer randomizer; the first group labeled “treatment group” and the second “control group.” The treatment group will receive post-operative treatment with pilocarpine 2% for 1 month postoperatively, in addition to the standard post-operative surgical drops including topical steroids and topical antibiotic drops. The control group will receive the usual post-operative drop schedule without pilocarpine. Most surgeons who do combined trabectome/cataract surgery will include the use of pilocarpine besides steroid and antibiotic. However, it is also acceptable for patients to only receive steroid and antibiotics (without pilocarpine) after such surgery. Patients in both groups will be followed for 1 year with the primary endpoint of percent decrease in IOP after surgery at 1 year. Secondary outcome measures will include: progression of glaucoma on OCT and HVF testing, medication side effects, number of pre and postoperative drops the patient was using before and after surgery, and need for further glaucoma surgery. All subsequent visits will be according to routine post-operative monitoring, where visual acuities, intraocular pressures, gonioscopy measurements will be performed at the slit lamp. These visits will coincide with standard of care post op follow up visits.

Participant recruitment

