3. Feasibility of study – Over the time period 2/2016 – 9/2017, [name] completed 118 combined cataract/trabectome surgeries. Based on her historical usage and her usage of the combined procedure only increasing due to its success, we believe 140 patients can be recruited over a 1.5 – 2 year time frame.

Analytic Plan

All analyses will be based on the intent-to-treat approach (ITT). Standard descriptive statistics will be used to summarize the baseline characteristics and outcomes of the two treatment arms. The primary endpoint, percent decrease in IOP at 1 year after surgery compared to baseline, will be analyzed by computing the mean difference of this endpoint between treatment groups (pilocarpine - no pilocarpine) along with the corresponding two-sided 95% confidence interval. Non-inferiority of treatment without pilocarpine will be declared if the upper limit of the two-sided confidence interval is less than the margin of non-inferiority, which is deemed to be 5% in this study. Since the ITT approach can be anti-conservative in non-inferiority trials, a per-protocol analysis will also be performed. Two sample tests of the standard null hypothesis of no difference between groups will be conducted using the student T-test

for continuous variables or chi-square test for categorical variables (e.g., occurrence of side effects, need for further surgery). Linear or logistic regression models will be fit to the data to adjust for any baseline characteristics which are found to differ between treatment arms. In addition, generalized linear mixed models will be fit to the repeated measures obtained post-surgery, as part of every standard clinic encounter during follow-up, to assess whether the longitudinal trends in the outcomes differ between groups.

Sample size considerations

The sample size for this study is 140 subjects (70 per group). This sample size will yield greater than 95% power at a 1-sided Type I error rate of 2.5% (two-sided of 5%) to declare non-inferiority of the no pilocarpine group to the pilocarpine group with respect to the percent decrease in IOP after surgery, assuming an alternative hypothesis of no difference between groups, a non-inferiority margin of 5%, and a SD of 7.5% in both groups based on prior studies.

Data and Safety Monitoring Policy

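### The primary 1-year comparison has no rule for a missing IOP, so by default it is an observed-case analysis rather than ITT, and its error rate depends on who is missing

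*Combined protocol and SAP*

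**What the plan says.** The Analytic Plan opens with "All analyses will be based on the intent-to-treat approach (ITT". The primary endpoint "will be analyzed by computing the mean difference of this endpoint between treatment groups", pilocarpine minus no pilocarpine, and non-inferiority is declared if the upper 95% confidence limit is below 5%. The same section adds: "Since the ITT approach can be anti-conservative in non-inferiority trials, a per-protocol analysis will also be performed". It then plans a further analysis: "In addition, generalized linear mixed models will be fit to the repeated measures obtained post-surgery", whose purpose is "to assess whether the longitudinal trends in the outcomes differ between groups". The 1-year non-inferiority decision is not tied to that model.

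On data collection, Study Methods says of the follow-up visits: "These visits will coincide with standard of care post op follow up visits". The Data and Safety Monitoring Policy says that a patient whose side effects are intolerable or unsafe stops the drug and leaves the study. Only the treatment group is assigned pilocarpine, for 1 month. The Consent section says that patients are not blinded.

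The documents give no expected dropout, no window for the 1-year visit, no imputation rule and no sensitivity analysis for missing data.

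**The concern.** A difference between two means with no imputation can use only patients whose 1-year IOP was recorded. Any randomised patient without that reading drops out of the decision, which is not what an ITT statement promises. The per-protocol analysis does not close the gap, because it needs the same reading.

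In a non-inferiority trial the consequence depends on who is missing. If poor responders are lost from both arms and the no-pilocarpine arm is truly worse, that arm loses more of its failures. The observed difference then shrinks and the false non-inferiority rate rises above 2.5%. If poor responders are lost only from the pilocarpine arm, that arm looks better than it is and the test becomes too strict. Earlier readings from the same patients will exist and could correct much of this, but the plan uses them only to describe trends.

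**Working it through.** **1. The plan's own figure.** Inputs from Sample size considerations: 70 per group, SD 7.5%, margin 5%, true difference 0, one-sided 2.5%.

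SE = 7.5 × √(2/70) = 1.268. Power = Φ(5/1.268 − 1.96) = 97.6% (97.5% with the t distribution). The stated power of more than 95% is reproduced.

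**2. Chance missingness.** The same formula with fewer patients (normal approximation) gives:

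- 63 per group (10% missing): 96.3%
- 59 (about 15%): 95.2%
- 56 (20%): 94.2%
- 49 (30%): 91.0%

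The stated power therefore needs about 59 observed 1-year values per group. The false non-inferiority rate stays near 2.5%.

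**3. Outcome-related missingness.** The documents give no rates, so everything here beyond 70 per arm, SD 7.5 and the 5-point margin is assumed. The true difference is set at the margin. One earlier visit correlates 0.5 or 0.7 with the 1-year value. Missingness is logistic in the earlier value, except in the last row of the table. There were 20,000 simulated trials per scenario.

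Hand check: if missingness shrinks the average raw difference by *b* points, the false non-inferiority rate is about Φ(−1.96 + b/SE). At 56 per arm, SE = 7.5 × √(2/56) = 1.417.

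The table is for 20% missing overall. Columns *b* and hand check use correlation 0.7. The simulated ranges cover correlations 0.5 to 0.7.

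| Who is missing | b | Hand check | Raw difference, simulated | Likelihood estimate, simulated |
|---|---|---|---|---|
| Chance | 0 | 2.5% | 2.4% | 2.3-2.4% |
| Poor early responders, both arms, log-odds slope 1 per SD | 0.39 | Φ(−1.685) = 4.6% | 3.6-4.7% | 2.4-2.5% |
| Same, slope 2 | 0.80 | Φ(−1.395) = 8.2% | 6.2-8.6% | 2.5-2.6% |
| Poor early responders, no-pilocarpine arm only | 1.10 | Φ(−1.184) = 11.8% | 7.7-11.6% | 2.3-2.5% |
| Poor early responders, pilocarpine arm only | −0.89 | Φ(−2.588) = 0.5% | 0.4-0.9% | 2.4-2.5% |
| Driven by the unseen 1-year value, both arms | 0.55 | Φ(−1.572) = 5.8% | 5.6-5.9% | 3.9-4.7% |

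**4. Range over 10-30% missing.** Loss from both arms at slope 1 gives about 3.5-5.5%, with the raw difference averaging 4.5-4.75 against a true 5. At slope 2 the rate reaches 10.4%. Loss related to response only in the no-pilocarpine arm gives 5.0-17.4%, and only in the pilocarpine arm 0.3-1.4%.

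**5. Weaker assumptions.** With 5% missing at slope 1 the rate is 2.9-3.0%. With 20% missing at slope 0.5 it is 2.8-3.0%. With 10% missing, slope 0.5 and correlation 0.5 it is 2.6%.

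**6. The termination rule alone.** With 10% missing by chance plus an extra 15% of terminations in the pilocarpine arm unrelated to IOP response, the rate is 2.5%.

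**The case against.** Five objections deserve weight.

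- **The completer set is not stated.** A reader might infer that the plan restricts the primary analysis to patients with a 1-year IOP. It does not say so. It says ITT and then is silent. The observed-case reading is a default, because a mean difference with no imputation leaves no other calculation. This stands, and the point is worded accordingly.
- **The harmful mechanism is assumed.** Nothing in the documents says that poor responders miss visits. A reader might infer that type I error is inflated, but the documents do not support that. Under chance missingness it is not, and under weak dependence the excess is a few tenths of a percentage point.
- **The one documented exit route points elsewhere.** Terminations for side effects fall on the pilocarpine arm. If unrelated to IOP response they leave the error rate at 2.5%; if they removed poor responders they would make the test conservative. This stands against any claim of one-directional bias. It does not remove the conflict with ITT.
- **The planned mixed model is not ready to use.** It is aimed at trends over irregular clinic visits. A 1-year contrast needs a time structure, a visit window and a covariance choice. The simulation used one fixed earlier visit, so it shows the principle and does not validate a particular model. This stands.
- **The model is not a full cure.** It leaves out patients with no post-surgery IOP and recovers little from those who leave in the first month. It removes only part of the error when missingness depends on the unseen value. This stands, and is why a sensitivity analysis is needed.

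A mixed-model contrast is one of several acceptable estimators. Leaving the choice open until the data are seen, in an open-label trial, is harder to defend.

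**Conclusion.** The concern holds in a limited form. The non-inferiority decision rests on a calculation that is observed-case by default and does not match the ITT statement, and the plan has no rule or sensitivity analysis for a missing 1-year IOP. The design is workable and the stated power is reproduced, but control of the 2.5% error rate rests on an unstated assumption that missingness is unrelated to IOP response.

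The size is conditional and the direction is open. The rate is near 2.5% under chance missingness and about 3.5-5.5% at 10-30% missing with moderate, response-related loss from both arms. It is higher with stronger dependence or loss confined to the no-pilocarpine arm, and below 2.5% if poor responders leave only the pilocarpine arm. The missing rates, correlations and strengths of dependence are illustrative assumptions.

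It should be settled in the SAP before outcomes are examined.

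**What to change.** - **Primary estimate.** Take the 1-year arm difference and its two-sided 95% confidence interval from a repeated-measures mixed model, using all randomised patients with any post-surgery IOP. Use percent decrease from baseline at each visit as the outcome, so that the result stays on the scale of the margin. Include arm, time window, arm-by-time and baseline IOP. Compare the upper limit with 5%.
- **Definitions.** State the 1-year visit window, the earlier time windows and the covariance structure in advance.
- **Supporting analysis.** Keep the raw difference in means.
- **Sensitivity analysis.** Add one tipping-point analysis that worsens the assumed outcome of missing no-pilocarpine patients step by step until the conclusion changes. This covers missingness that observed readings do not explain.
- **Reconciliation.** The termination rule in the Data and Safety Monitoring Policy and the ITT statement in the Analytic Plan must be reconciled. Report the number missing at 1 year by arm and reason.

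The cost is SAP text and some specification work, with no new patients or visits. The small downside is that the result depends on a model and a pre-set window, and patients with few or no post-surgery readings contribute little or nothing.

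### The per-protocol analysis added because ITT can be anti-conservative has no stated role in the non-inferiority decision, and the plan has no rule for discordant results

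*Combined protocol and SAP*

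**What the plan says.** The Analytic Plan opens with "All analyses will be based on the intent-to-treat approach (ITT"). The primary endpoint is the percent decrease in IOP from baseline to 1 year, compared as the mean difference, pilocarpine minus no pilocarpine, with a two-sided 95% interval. The decision rule is: "Non-inferiority of treatment without pilocarpine will be declared if the upper limit of the two-sided confidence interval is less than the margin of non-inferiority". The margin is set at 5%. The next sentence reads "Since the ITT approach can be anti-conservative in non-inferiority trials, a per-protocol analysis will also be performed". The per-protocol analysis is not mentioned again.

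The Sample size considerations section powers one comparison: 70 per group, SD 7.5%, margin 5%, true difference zero, one-sided 2.5%, power above 95%.

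Two other sections bear on the point. Consent says that patients are not blinded. The Data and Safety Monitoring Policy says that when a side effect cannot be tolerated, or continuing is judged unsafe, the drug is stopped and the patient's participation in the study ends.

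**The concern.** The plan names a hazard and a safeguard, then leaves the safeguard out of the rule that produces the conclusion. The rule refers to one interval, and the opening sentence makes that interval ITT. A result with an ITT upper limit below 5% and a per-protocol upper limit above 5% meets the rule as written.

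The hazard is plausible here. Pilocarpine patients who skip or stop drops, and control patients who receive pilocarpine, pull the ITT difference toward zero, which is the favourable direction in this trial. The Background describes pilocarpine as needing frequent dosing and causing many side effects, and discontinuation for adverse effects is one of the Key Questions. Study Methods says most surgeons use pilocarpine after this operation, so a non-inferiority claim would argue against common practice. If the two analyses disagree, investigators who have seen unblinded results would have to decide how much weight the second one gets.

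**Working it through.** **Inputs from the plan.** n = 70 per arm, SD = 7.5, margin = 5 points, one-sided 2.5%, true difference 0 for power.

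**Inputs assumed.** Non-adherence f = 10%, 20% or 30% of the pilocarpine arm. Non-adherent patients respond like controls, stay in follow-up, and do not differ in prognosis.

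**Step 1: the plan's own power.** SE = 7.5 × √(2/70) = 1.268. Power ≈ Φ(5/1.268 − 1.960) = Φ(1.984) = 97.6%. The noncentral t with 138 df gives 97.5%. The plan's figure of more than 95% is reproduced.

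**Step 2: error for the effect as assigned.** At a true ITT difference of exactly 5, the upper limit falls below 5 in 2.5% of trials. Non-adherence does not change this.

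**Step 3: error for the effect in adherent patients.** Let that effect be exactly 5 points. The ITT difference is then 5(1 − f), and the chance that the rule is met is about Φ(5f/1.268 − 1.960).

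| f | ITT difference | Normal formula | Noncentral t, SD 7.5 | Simulation, mixed arm |
|---|---|---|---|---|
| 10% | 4.5 | Φ(−1.566) = 5.9% | 5.8% | 5.6% |
| 20% | 4.0 | Φ(−1.171) = 12.1% | 12.0% | 11.2% |
| 30% | 3.5 | Φ(−0.777) = 21.9% | 21.6% | 20.5% |

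The simulation (200,000 trials per row; 7, 14 or 21 non-adherent patients) includes the extra spread from mixing adherent and non-adherent patients in one arm. If the number of non-adherent patients varies at random, the results are 5.8%, 11.7% and 20.8%. About 5.6%, 11% and 21% is a fair summary.

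In the same simulation, requiring the per-protocol upper limit to be below 5 as well brings the rate to about 2.5% in every row. ITT passes while per-protocol fails in about 3%, 9% and 18% of trials. That is the outcome for which the plan has no rule.

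**Step 4: power of the joint rule, true difference 0.** Simulated with the per-protocol set nested in the ITT set:

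| Excluded | Both arms (per-protocol n) | Pilocarpine arm only |
|---|---|---|
| 10% | 95.7% (63 and 63) | 96.5% |
| 20% | 93.4% (56 and 56) | 95.4% |
| 30% | 90.1% (49 and 49) | 94.0% |

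With equal exclusions, joint power is already 94.9% at 60 per arm.

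**Step 5: the two sections side by side.** The Analytic Plan says ITT for all analyses. The Data and Safety Monitoring Policy ends participation for patients taken off the drug. If those patients have no 1-year IOP, they cannot dilute the ITT mean as in Step 3, and the ITT and per-protocol sets nearly coincide for that group. Step 3 would then apply only to patients who skip drops but stay in; control patients given pilocarpine would dilute the difference in the same way. The documents do not say which situation holds.

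**The case against.** The strongest reply is that the plan never says ITT alone decides. The sentence that adds the per-protocol analysis gives anti-conservatism as its reason, and a fair reader could take it to mean that the same margin applies there. That stands to this extent: the per-protocol result is not barred from influencing interpretation; it has no stated role. The gap is silence on discordance, and the rule as worded is still met by the ITT interval.

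A reader might infer that the trial's real type I error exceeds 2.5%. The documents do not support that. Objective 1 compares surgery without pilocarpine with surgery followed by pilocarpine, and the analysis is as assigned. A true ITT difference of 4.5, 4.0 or 3.5 lies inside the margin, so declaring non-inferiority there is correct. The Step 3 rates are errors only if the target is the effect in adherent patients.

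A reader might also infer that per-protocol is the safer analysis. It is not automatically so: its exclusions can break randomization, in an unblinded trial, and the 2.5% under the joint rule depends on non-adherence being unrelated to prognosis. This is a reason to require both analyses, not to replace one with the other.

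Finally, the non-adherence rates are assumed, the pilocarpine course lasts only one month, and a stated rule for discordant results would also close the gap. All of that is true. The joint rule is recommended because it follows most directly from the plan's own reason for adding the second analysis.

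**Conclusion.** The point holds as a gap in the decision rule. There is no arithmetic error, and the sample-size figure is sound. The plan's stated safeguard has no stated part in the conclusion, its analysis set is undefined, and a discordant result has no rule.

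The size is conditional: about 5.6%, 11% or 21% instead of 2.5%, if the target is the effect in adherent patients, that effect sits exactly at 5 points, and 10%, 20% or 30% of the pilocarpine arm do not adhere but remain in follow-up. These figures show sensitivity and do not predict this trial's error rate. They overstate the dilution to the extent that patients who stop the drug leave follow-up. The change should be made because it concerns the primary claim and needs no more patients on the plan's own inputs, provided the lower joint power is accepted.

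**What to change.** 1. In the Analytic Plan, replace the rule with: non-inferiority of treatment without pilocarpine will be declared only if the upper limit of the two-sided 95% confidence interval is below 5% in both the ITT and the per-protocol analysis.
2. Define the per-protocol set from data already recorded at visits, such as assigned arm, drops in use, and pilocarpine stopped for side effects. Fix it before 1-year IOP is compared by arm. The protocol describes no adherence measure, so a finer definition would need extra data collection.
3. Reconcile the Data and Safety Monitoring Policy with the ITT statement, so that it is clear whether the 1-year IOP of patients whose participation ends is in the ITT set. Without this, the second analysis may add little for those patients.
4. Restate the power for the joint rule, with the assumed exclusions.

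**Cost.** Protocol and SAP wording. Joint power falls from 97.5% to about 96%, 93% or 90% with 10%, 20% or 30% excluded from both arms, or about 96.5%, 95% or 94% if only the pilocarpine arm loses patients. The claim of more than 95% would not survive 20% exclusions in both arms. Per-protocol exclusions can also introduce bias, so both intervals should be reported whatever the outcome.

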Pilocarpine, a parasympathomimetic agent, is a glaucoma medication that works by causing contraction of the ciliary muscle leading to opening of the trabecular meshwork[3]. Due to its frequent dosing requirement and large number of ocular and systemic side effects, pilocarpine has largely fallen out of favor for the treatment of primary open angle glaucoma (POAG), except in patients for whom few other alternatives exist. However, pilocarpine is often used after trabectome surgery. The rational for its use after Trabectome procedure is for its miotic effect, which theoretically may prevent the formation of peripheral anterior synechiae. Formation of peripheral anterior synechiae can lead to the closure of the cleft that is generated and the possibility of failure of the procedure. While the theoretical benefit of pilocarpine has been proposed, its actual benefit has never been proven. In this study, we aim to evaluate whether Trabecome / Cataract surgery without pilocarpine is non-inferior to Trabecome / Cataract surgery procedure followed by treatment with pilocarpine. The outcomes to be evaluated are the degree (percentage) of IOP lowering from baseline after the procedure, the mean post-operative IOP, the number of IOP lowering agents required to achieve goal IOP, and the rate of progression towards further glaucoma surgeries.

Key Questions

1. What are the demographics and characteristics of patients undergoing combined cataract/trabectome surgery at Montefiore Medical Center?
2. What is the post procedure percent IOP drop at 1 month, 6 months and 1 year after surgery.

3. What is the number of pre and post procedure drops required to achieve goal IOP at 6 months, 1, 2 and 3 years after combined cataract/trabectome surgery in patients treated with post-op pilocarpine vs control?
4. What is the rate of progression towards further surgery in patients treated with post-op pilocarpine vs control over a 3 year follow up period?
5. What is the rate of pilocarpine related side effects and drug discontinuation due to adverse effects?

Objectives

1. To determine whether Trabectome/cataract surgery without pilocarpine is non-inferior to Trabecome / Cataract surgery procedure followed by treatment with pilocarpine in decreasing IOP at 1 year after surgery.
2. To determine the incidence and characteristics of pilocarpine induced side effects in this population.

Selection of Patients

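### The pre-operative drop count enters the between-arm comparison of drops only if the arms happen to differ on it, so most of the available precision gain on this secondary outcome is lost

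*Combined protocol and SAP*

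**What the plan says.** Study Methods lists among the secondary outcomes the "number of pre and postoperative drops the patient was using before and after surgery". Key Questions, item 3, asks "What is the number of pre and post procedure drops required to achieve goal IOP at 6 months, 1, 2 and 3 years", comparing pilocarpine with control. The Background also lists the number of IOP-lowering agents among the outcomes to be evaluated.

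The Analytic Plan has no analysis specific to drops. Three of its statements bear on them:

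- The general between-arm test: "Two sample tests of the standard null hypothesis of no difference between groups will be conducted using the student T-test" (for continuous variables, with chi-square for categorical ones).
- Adjustment: "Linear or logistic regression models will be fit to the data to adjust for any baseline characteristics which are found to differ between treatment arms".
- Longitudinal analysis: "generalized linear mixed models will be fit to the repeated measures obtained post-surgery", to see whether trends differ between groups.

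The plan does not say whether a t-test for drops would use the post-operative count or the change from before surgery. It does not say how a baseline difference is to be detected. It names no baseline covariate for the mixed model.

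**The concern.** A baseline covariate improves precision because it predicts the outcome, not because it is imbalanced. A rule that adjusts only for characteristics on which the arms differ selects on the wrong property: a pre-operative count that is balanced but strongly predictive is left out. The choice of model also comes to depend on the data, through a check that the plan does not define.

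This matters because of what the drop count shows. If pressure is treated towards a goal, similar IOP in the two arms could be reached with more medication in one of them, and the drop count is where that would appear. Risks and Benefits gives a lower medication burden as a benefit of omitting pilocarpine. The 140 patients were sized on percent IOP decrease alone, so any precision for drops has to come from the analysis.

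**Working it through.** **The plan's own figure.** Sample size considerations gives 70 per group, margin 5%, SD 7.5%, no true difference and one-sided 2.5%. Then 5 / (7.5 × √(2/70)) = 3.944, and Φ(3.944 − 1.960) = 97.6% (97.5% with the noncentral t). This agrees with the stated power above 95%. It concerns the primary IOP endpoint and has no bearing on drops.

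**Inputs for drops.** From the documents: 70 per arm and two-sided 5%. Assumed, because the documents do not give them: a true difference of 0.4 SD of the post-operative count, a pre/post correlation ρ of 0.3 to 0.7, no dropout, and approximately normal theory. The change-score figures also assume equal pre- and post-operative SDs.

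**Formulas.** With 70 per arm the noncentrality is d × √(70/2) = 5.916 × d. The effective d is:

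- post-operative count, unadjusted: 0.4
- adjusted for the pre-operative count: 0.4 / √(1 − ρ²)
- change from baseline: 0.4 / √(2(1 − ρ))

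**Power (noncentral t).**

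| ρ | t-test, post-operative count | Adjusted for pre-operative count | t-test, change |
|---|---|---|---|
| 0.3 | 65% | 69% | 51% |
| 0.5 | 65% | 77% | 65% |
| 0.7 | 65% | 91% | 86% |

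At ρ = 0.5, for example, the adjusted noncentrality is 5.916 × 0.4 / √0.75 = 2.73, against 5.916 × 0.4 = 2.37 unadjusted.

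**Precision.** Adjustment multiplies the variance of the arm difference by 1 − ρ², which is 0.91, 0.75 or 0.51 at ρ = 0.3, 0.5 or 0.7. The interval is narrower by 1 − √(1 − ρ²), or about 5%, 13% or 29%. The equivalent sample size is 70 / (1 − ρ²), or about 77, 93 or 137 per arm. At ρ = 0.1 the factor is 0.99 and the gain is negligible.

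**How much the conditional rule recovers.** The plan gives no trigger, so p < 0.05 on the baseline count is assumed. Under randomization it fires in about 5% of trials. Simulation (20,000 trials per ρ, normal data, 70 per arm) gave these variances, where 1 is the theoretical unadjusted value:

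| ρ | Adjust only if arms differ | Always adjust |
|---|---|---|
| 0.3 | 0.99 | 0.92 |
| 0.5 | 0.93 | 0.75 |
| 0.7 | 0.86 | 0.50 |

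At ρ = 0.5 the rule recovers about 0.07 of an available 0.25, roughly a quarter. Simulated power at 0.4 SD under the rule was about 66%, 66% and 67–68% at ρ = 0.3, 0.5 and 0.7, little above the unadjusted 65%.

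**The case against.** A reader might infer that the collected baseline is simply unused. The documents do not support that. Baseline characteristics are to be summarised. The sentence directly after the t-test provides regression adjustment, which would bring in the pre-operative count if the arms differed on it. Since Study Methods and Key Question 3 both speak of pre and post counts, a t-test on change is also a natural reading, and it would use the baseline. What remains is that none of these routes is both fixed in advance and efficient. With equal SDs, change is less precise than the post-operative count alone when ρ is below 0.5, and it is never more precise than adjustment. With unequal SDs that threshold becomes SD_pre / (2 × SD_post), so the change-score figures could move either way.

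The mixed model is a further analysis, and repeated measures may add information that a single-visit power comparison misses. That is fair. But it covers post-surgery measurements, names no baseline covariate and is aimed at trends.

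Applying the t-test to drops is itself an inference, since the plan assigns no test to them. That stands, and it makes this partly a matter of under-specification.

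It is also fair that the effect size and ρ are assumed, that an operation meant to reduce medication might leave ρ low, and that at ρ = 0.3 the gain is only about 4 points.

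A reader might go further and infer bias, or a threat to the non-inferiority conclusion. Neither follows. Randomization keeps the unadjusted comparison unbiased, Objective 1 concerns IOP only, and no margin or power claim is attached to drops.

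**Conclusion.** The concern holds as a loss of precision on one secondary outcome. The pre-operative count enters the comparison of drops only through an undefined imbalance check, or through a change score that the plan does not specify. If the t-test is on the post-operative count and the trigger is p < 0.05, about three quarters of the available variance reduction is lost. If it is on change with equal SDs, the power lost relative to adjustment is about 18, 12 and 5 points at ρ = 0.3, 0.5 and 0.7.

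Routine adjustment would raise power over the post-operative t-test by about 4, 12 or 26 points at those correlations. These sizes are illustrative, because they depend on the assumed 0.4 SD difference and on ρ. The direction does not: adjustment helps to the extent that the two counts are correlated, and otherwise costs almost nothing. This is a free improvement to the plan, not an error that invalidates a result.

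**What to change.** In the Analytic Plan, add for this outcome: *The number of IOP-lowering drops at each follow-up time point analysed will be compared between arms by a linear model with treatment arm and pre-operative number of drops, using robust standard errors, and the adjusted mean difference with its 95% confidence interval will be reported. The pre-operative number of drops will be included whether or not the arms differ on it, and will also be a covariate in the mixed model for drops.*

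This also settles the choice between post-operative count and change in advance. The robust standard errors allow for an outcome that is a small whole number. The cost is two sentences and one degree of freedom in the linear model, with no new data, visits or patients.

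The wording leaves the time points open on purpose. Key Question 3 asks about 2 and 3 years while Study Methods gives 1 year of follow-up. That is a separate inconsistency, to be reconciled on its own.
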